**NOTES:**

- Additional parameters may be included as required.
- No log transformation for  $T_{\max}$  nor any ratio (relative) endpoint.
- [1]:  $AUC_{(0-t)}$  if  $AUC_{(0-\infty)}$  cannot be derived
- [2]: If BID formulation.
- [3]: QD formulation only.

### 8.2.2. Summary Measure

For each fed/faasted state in Parts A and C, and for day 1 and day 3 of every dose (period) in Part B, descriptive statistics (n, arithmetic mean, standard deviation [SD], 95% CI, minimum, median and maximum,) will be calculated by treatment for all PK concentrations over time and for the derived PK parameters. In addition, for loge-transformed PK parameter variables geometric mean, 95% CI and % $CV_b$  will be provided, where % $CV_b$  =  $(100 * \sqrt{(\exp(SD^2) - 1)})$  and SD is the standard deviation of log-transformed data.

For Part B, log-scale dose normalized  $C_{\max}$ ,  $C_{12h}$  (for BID),  $C_{24h}$ ,  $AUC_{(0-12)}$  (for BID dosing)  $AUC_{(12-24)}$  (for BID dosing), and  $AUC_{(0-24)}$  will also be summarized. Plots of dose vs log-scale dose normalised  $AUC_{(0-24)}$ , ( $AUC_{(0-12)}$  and  $AUC_{(12-24)}$  for BID dosing),  $C_{12h}$  (for BID),  $C_{24h}$ , and  $C_{\max}$  (after morning and evening doses if BID dosing) will be generated to determine if there are any dose dependent changes in the absorption of GSK2982772 following repeat dose administration of the selected minitab MR formulation.

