Following completion of Parts A and B, it was determined that the slowest minitab formulation provided a PK profile suitable for QD dosing but this formulation was susceptible to a food effect. Therefore, Part C of the study will investigate MR tablet formulations at up to 4 different dose levels in the fasted state. The 240 mg tablet will have a fixed composition which will have a dissolution profile similar to the slowest minitab; however, for the 360 mg and 480 mg tablets polymer compositions may be adjusted as part of a ‘design space’ concept to try to optimize the in vivo performance of 360 mg and /or 480 mg tablets based on the PK of the 240 mg MR tablet formulation. This adjustment will be done ahead of dosing to select a formulation at each dose unit to achieve an adjusted in vivo profile based on the PK of the 240 mg MR tablet formulation. The effect of food (standard meal) will then be investigated at either the 240 mg, 360 mg or 480 mg dose level with the option to evaluate the effect of a high fat or a delayed standard meal, to determine whether GSK2982772 can be administered with or without a food restriction in the planned proof of concept study. Although the target dosing regimen is QD, if a food effect is observed or the single dose exposure profile is not appropriate for QD dosing, BID dosing may be investigated. Dosing of multiple dose units may also be investigated.

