Part B of the study will be an open-label, repeat dose study in which the selected MR minitab formulation in a capsule will be evaluated following 3 days repeat dosing of GSK2982772 at target daily doses of 30, 60 and 240 mg (Figure 3). The target dose may be subject to change based upon evaluation of the emerging data from Part A, e.g. if the bioavailability of 120 mg MR formulation in a capsule is less than the 120 mg IR tablet (reference) formulation. In Part B, administration of the MR minitab formulation in a capsule will either be in the fasted state or with a standard meal (non-high fat), depending on the results of the food effect assessment in Part A. The prandial state for each dosing period may be selected as fasted or fed (standard meal) but within each dosing period, all doses will be administered in the same prandial state. The frequency of dosing in Part B will either be QD or BID depending on the PK profile in Part A. Whether dosing is QD or BID, the total daily doses will remain the same. If BID dosing is selected the final dose will be the evening dose of Day 3. Participants will be admitted to the clinic in the morning of the day before dosing (i.e. Day -1) of each inpatient period. Each inpatient period will consist of 5 days and 4 nights. There will be a minimum of 7 days washout between the last morning dose of one period and the first dose of the next period. A follow-up visit will occur at least 7 days after the last study treatment.

Figure 3 Part B Study Design – Dose Ranging

Part C of the study is a non-randomised 6 period, sequential, fixed sequence crossover design in which MR tablet formulations will be evaluated (Figure 4). Periods 1 and 2 will evaluate single dose administration of a 240 mg MR tablet in the fasted state and the 240 mg IR tablet (reference), respectively. Periods 3, 4, 5 and 6 will be flexible and the dosing regimen will be dependent on the outcome of Periods 1 and 2. In Periods 3 to 6, there will be the option to evaluate higher doses, the impact of a high-fat meal and/or standard meal after dosing or BID dosing.

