## 5. CONSIDERATIONS FOR DATA ANALYSES AND DATA HANDLING CONVENTIONS

### 5.1. Study Treatment & Sub-group Display Descriptors

Treatment Group Descriptions			
RandAll NG		Data Displays for Reporting	
Code	Description	Description	Order in TLF
Part A			
A	GSK2982772 120mg minitab MR RR1 oral single dose	MT-12h 120mg Fasted	2
B	GSK2982772 120mg minitab MR RR2 oral single dose	MT-8h 120mg Fasted	3
C	GSK2982772 120mg IR oral single dose	IR 120mg Fasted	1
D	GSK2982772 120mg minitab MR RR3 oral single dose	MT-12h 120mg Fed (Standard)	4
E	GSK2982772 120mg minitab MR RR4 oral single dose	n/a	5
F	GSK2982772 120mg minitab MR fed state	n/a	6
Part B			
G	GSK2982772 minitab MR Repeat Dose 1	MT-12h 120mg Fasted	1
H	GSK2982772 minitab MR Repeat Dose 2	MT-12h 240mg Fasted	2
J	GSK2982772 minitab MR Repeat Dose 3	MT-12h 300mg Fed (Standard)	3
Part C			
K	GSK2982772 240mg (matrix monolithic) MR oral single dose	MM-12h 240mg Fasted	2
L	GSK2982772 240mg IR oral single dose	IR 240mg Fasted	1
M	GSK2982772 360mg or 480mg (matrix monolithic) MR oral single dose	MM-12h 480mg Fasted	3
N*	GSK2982772 240mg (matrix monolithic) MR fed state	MM-12h 480mg Fed (Standard)	4
P	GSK2982772 360mg or 480mg (matrix monolithic) MR delayed fed (standard meal) or fed (high-fat meal)	MM-12h 480mg Delayed Fed (Standard)	5
Q	GSK2982772 dose tbd (matrix monolithic) MR QD or BID prandial state tbd.	MM-12h 240 mg Delayed Fed (High-Fat)	6

\* The randomization description for Period 4 of Part C (code N) indicates 240 mg, but the label has been updated to 480 mg to reflect the actual treatment administered.

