## Bioavailability of Dose

Endpoint (log scale)

 
• <math>AUC(0-\infty)</math>
 
• <math>AUC(0-t)</math> if <math>AUC(0-\infty)</math> not available
 
• <math>AUC(0-24)</math>
 
• <math>C_{max}</math>
 
• <math>C_{24}</math>
 

Model Specification

 
• For each endpoint a mixed model will be fit with 2 observations per subject expected. The model will contain dose (480 mg and 240 mg in the fasted state) as a fixed, categorical effect, and a random intercept for subject.
 
• The Kenward and Roger method for approximating the denominator degrees of freedom and correcting for bias in the estimated variance-covariance of the fixed effects will be used.
 

Model Checking & Diagnostics

See Section 8.1.5.1.

Model Results Presentation

Point estimates and corresponding 90% CI will be computed for the differences in the endpoint for GSK2982772 MR dose (480 mg vs 240 mg) using the residual error from the model (MSE).

The point and interval estimates on the log-scale will then be exponentially back transformed to give estimates of the ratios of geometric means, <math>F_{relDOSE}</math>, and 90% CI. See Section 10.6.4

Endpoint

Tmax

Model Specification

Exact non-parametric Hodges-Lehmann estimation of location shift will be fitted.

Only GSK2982772 administered at 240 mg and 480 mg.

Model Results Presentation

GSK2982772 MR formulation at 480 mg (test) state will be compared to 240 mg (reference).

Median difference and 90% CI for median difference will be presented.

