## 10.11.7.2. Pharmacokinetic Tables Part B

Pharmacokinetic: Tables					
No.	Population	IDSL / TST ID / Example Shell	Title	Programming Notes	Deliverable [Priority]
PK Concentration					
3.8.	PK	PK01	Summary of Plasma GSK2982772 Pharmacokinetic Concentration-Time Data by Dose and Day: Part B		SAC
PK Derived Parameters					
3.9.	PK	PKPT1	Summary Statistics of Derived Plasma GSK2982772 Pharmacokinetic Parameters by Dose and Day: Part B	Parameters with units	SAC
3.10.	PK	PKPT3	Summary Statistics of Log-Transformed Derived Plasma GSK2982772 Pharmacokinetic Parameters by Dose and Day: Part B	Parameters with units	SAC
3.11.	PK	PKPT3	Summary Statistics of Log-Transformed Derived Plasma GSK2982772 Dose-Normalized Pharmacokinetic Parameters by Dose and Day: Part B	Parameters with units	SAC
PK Analyses					
3.12.	PK	PK_T2	Summary of Statistical Analysis of Plasma GSK2982772 PK Parameters (AUC & C) Assessing Relative Bioavailability of Repeat Dose: Part B		SAC

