### 10.11.8.2. Pharmacokinetic Figures Part B

Pharmacokinetic: Figures					
No.	Population	IDSL / TST ID / Example Shell	Title	Programming Notes	Deliverable [Priority]
Individual Concentration Plots					
3.8.	PK	PKCF1P	Individual GSK2982772 Plasma Concentration-Time Plot by Subject (Linear and Semi-Log): Part B	Paginate by Subject	SAC
3.9.	PK	PKCF1P	Individual GSK2982772 Plasma Concentration-Time Plot by Dose (Linear and Semi-Log): Part B	Paginate by Dose	SAC
Mean / Median Concentration Plots					
3.10.	PK	PKCF2	Mean Plasma GSK2982772 Concentration-Time Plots by Dose (Linear and Semi-log): Part B	Paginate by Dose	SAC
3.11.	PK	PKCF3	Median Plasma GSK2982772 Concentration-Time Plots by Dose (Linear and Semi-log): Part B	Paginate by Dose	SAC
3.12.	PK	PK_F1	Plot of Individual Subject (+Geometric Mean and 95% CI) Plasma GSK2982772 Dose-Normalized PK Parameters vs Dose: Part B		SAC
3.13.	PK	PK_F2	Plot of Geometric Mean Ratio and 90% CI of Plasma GSK2982772 PK Parameters Assessing Relative Bioavailability of Repeat Dose: Part B		SAC

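### Part B reads dose-dependent absorption across 120, 240 and 300 mg, but 300 mg is the only fed level, so only 240 vs 120 mg is free of food

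*SAP*

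**What the plan says.** SAP 8.2.2 plans Part B summaries of log-scale dose-normalised exposure, and plots of it against dose, which "will be generated to determine if there are any dose dependent changes in the absorption of GSK2982772 following repeat dose administration" of the selected minitab formulation. This serves a named secondary objective (SAP 2.2). The section does not restrict the reading to fasted levels and gives no caveat about food.

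The displays are Table 3.11 ("Dose-Normalized Pharmacokinetic Parameters by Dose and Day: Part B") and Figure 3.12 ("Plasma GSK2982772 Dose-Normalized PK Parameters vs Dose: Part B"). Neither title mentions prandial state, and no shell is visible.

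SAP 5.1 gives the regimens as administered. The 120 mg and 240 mg levels are both labelled fasted, and the third is "MT-12h 300mg Fed (Standard"). Protocol 5.1 foresaw this kind of outcome: "The prandial state for each dosing period may be selected as fasted or fed (standard meal"), with one state for all doses within a period. Protocol 3.1 reports that the slowest minitab gave a profile suitable for once-daily dosing but that "this formulation was susceptible to a food effect".

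The Part B model in SAP 8.2.5.2 has dose, day and their interaction, with no prandial term. Its reported contrasts are Day 3 against Day 1 within each dose.

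In Part C the SAP handles the same question differently. For AUC, Cmax and C24, "The model will contain dose (480 mg and 240 mg in the fasted state) as a fixed, categorical effect".

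**The concern.** A plot of dose-normalised exposure against dose answers the dose question only if nothing else changes with dose. Here the meal changes at exactly one level, the top one, and the formulation is known to respond to food. Read as SAP 8.2.2 directs, a higher or lower dose-normalised value at 300 mg would be reported as dose-dependent absorption when the meal alone could have caused it. Equally, a real departure from proportionality at 300 mg could be cancelled by the meal and reported as proportional.

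Protocol 5.4 says the repeat-dose levels were run to check that the formulation can deliver an exposure range supporting the Phase IIb dose-ranging studies. A wrong statement about dose dependence would bear on that use.

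**Working it through.** **1. Can food and dose be separated in Part B?** Write the design with an intercept, an indicator for 240 mg, an indicator for 300 mg, Day 3 and fed. The fed column equals the 300 mg column in every row. The matrix has 5 columns and rank 4, and dropping fed also leaves rank 4. The aliasing is complete. It comes from the regimens in SAP 5.1 and does not depend on sample size.

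**2. What a reader would see.** Let *d* be the true ratio of dose-normalised exposure at 300 vs 120 mg, and *g* the fed/fasted ratio. The apparent ratio is *d* × *g*. The documents do not give *g*, so these values are assumptions:

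- *d* = 0.80, *g* = 1.25: apparent 1.00
- *d* = 1.25, *g* = 0.80: apparent 1.00
- *d* = 1.00 (no dose dependence): apparent ratio equals *g*

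For the last case, take a least-squares line of log dose-normalised exposure on log dose at 120, 240 and 300 mg. The weights are −1.175, 0.343 and 0.832, so the false slope is 0.832 × ln *g*:

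| Assumed *g* | False slope |
|---|---|
| 0.80 | −0.19 |
| 1.25 | +0.19 |
| 1.60 | +0.39 |
| 2.00 | +0.58 |

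The SAP plans no such slope. It simply puts a number on what the eye would take from the plot. The 240 vs 120 mg comparison carries none of this.

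**3. What is given up by leaving 300 mg out of the trend.** The dose range falls from 300/120 = 2.5-fold to 240/120 = 2-fold. The step lost is 300/240 = 1.25-fold.

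**4. Precision of the fasted contrast.** Protocol 10.2.2 gives within-subject CVs of 17.6% (AUC) and 23.2% (Cmax), and precision at N = 8 of 12.1% and 16.7%. The formula exp(t(0.95, 7) × √ln(1+CV²) / √8) − 1 returns 12.4% and 16.6%, close to those figures. For a paired ratio of two regimens the multiplier is √(2/n), so the 90% CI around an observed ratio of 1.00 is exp(± t(0.95, n−1) × √(2/n) × √ln(1+CVw²)):

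| CVw | n = 6 | n = 8 | n = 10 |
|---|---|---|---|
| 17.6% | 0.82–1.23 | 0.85–1.18 | 0.87–1.15 |
| 23.2% | 0.77–1.31 | 0.81–1.24 | 0.83–1.21 |
| 30.9% | 0.70–1.42 | 0.75–1.33 | 0.78–1.28 |

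Here n = 6 is the minimum evaluable number and n = 10 the number enrolled. The 30.9% row is the AUC figure in Protocol 10.2.3, derived from the largest Part A between-subject CV, and serves as an upper check.

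**5. Why both Part B CVs are carried.** Protocol 10.2.2 appears to exchange AUC and Cmax between two sentences. The variance ratio ln(1+CVw²)/ln(1+CVb²) is 0.25 for AUC (17.6 vs 36.1) and 0.74 for Cmax (23.2 vs 27.1) as labelled. With the labels exchanged it is 0.43 for both pairs. Protocol 10.2.3 also gives 0.43 for both parameters (30.9 vs 48.7; 36.7 vs 58.5). The documents do not show which sentence is at fault. The aliasing does not depend on it.

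**The case against.** The strongest reply is that nothing inferential is planned. SAP 2.4 says no formal hypothesis will be tested, Protocol 10.4.1 calls the Part B endpoints descriptive, and the only modelled contrasts are Day 3 vs Day 1. The disputed sentence repeats protocol text written before doses and prandial states were fixed. Displays by treatment may well carry the fed label from SAP 5.1, so a careful reader would be warned. On this view a single caveat is enough.

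Much of this is true, and it limits the severity. It does not remove the point. SAP 8.2.2 states what the plots are for, and a label on an axis does not say which comparison supports that conclusion.

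Four narrower objections also have force:

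- The Part C restriction applies to the AUC, Cmax and C24 model. The Part C Tmax comparison of doses states no fasted restriction, so the SAP has no uniform rule.
- The fasted 240 vs 120 mg contrast is free of food but not of period, because SAP 8.2.5.2 ties each dose to one period.
- The Day 3 vs Day 1 ratios share one prandial state, but meal timing is not identical. Under Protocol 6.3.1, fasted Part B participants get breakfast about 2 hours after the Day 2 dose, whereas food is otherwise withheld until about 4 hours after fasted dosing.
- A dose contrast added now is post hoc, since Protocol 3.1 says Parts A and B were complete before Part C was planned.

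**Conclusion.** The concern holds. As written, SAP 8.2.2 can report a meal effect at 300 mg as a dose effect, or hide a real dose effect there. The aliasing is certain given the SAP 5.1 labels. Its practical size is unknown because the documents do not quantify the food effect, so the ratios and slopes above are illustrations.

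The comparison free of food is 240 vs 120 mg. Its approximate 90% limits around 1.00 run from 0.77–1.31 (n = 6, CVw 23.2%) to 0.87–1.15 (n = 10, CVw 17.6%), and wider if the Part A variability applies. These rest on a simple paired calculation, not the planned covariance structure, and the Part B CVs come from a 20 mg immediate-release capsule.

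This should be fixed, but it is not critical: the objective is secondary and descriptive, and the Day 3 vs Day 1 contrasts do not mix fed and fasted states.

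**What to change.** - **SAP 8.2.2:** state that Part B dose dependence is read from the two fasted levels only.
- **SAP 8.2.5.2:** for the modelled AUC and Cmax endpoints, add the dose-normalised 240 vs 120 mg ratio with 90% CI on Day 1 and Day 3. This is the log least-squares mean difference minus ln 2 = 0.693. Describe it as added after the Part B data were available, and note that dose is tied to period. C12h (if BID) and C24h are not in that model and stay descriptive.
- **Figure 3.12 and Table 3.11:** keep 300 mg, mark it fed, place it outside the dose trend, and note that dose and food cannot be separated there.
- **Exploratory Part B standard-meal effect (Protocol 10.4.1):** label any dose-corrected estimate as conditional on dose proportionality, since it rests on the same aliased comparison.
- **Before using Part A as evidence on the meal effect:** reconcile the meal type. Protocol 4 and 7.1.1 and SAP 2.2 describe a high-fat meal, while SAP 5.1 has "MT-12h 120mg Fed (Standard"). Part A was also single-dose and in different people (Protocol 6.2, criterion 22).

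The core cost is one sentence, one contrast on two days from a planned model, and a note on one figure and one table. The downside is a dose statement covering only a 2-fold fasted range, with wide intervals at n = 6 to 10.

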### 8.2.3. Population of Interest

The secondary pharmacokinetic analyses will be based on the Pharmacokinetic population, unless otherwise specified.

### 8.2.4. Strategy for Intercurrent (Post-Randomization) Events

- See Section 8.1.4.

### 8.2.5. Statistical Analyses / Methods

Details of the planned displays are provided in [Appendix 11](#): List of Data Displays and will be based on GSK Data Standards and statistical principles.

Unless otherwise specified, endpoints / variables defined in Section 8.2.1 will be summarised using descriptive statistics, graphically presented (where appropriate) and listed.

### 8.2.5.1. Statistical Methodology Specification (Part A)

Endpoint (log scale)

 
• <math>AUC_{(0-\infty)}</math>
 
• <math>AUC_{(0-t)}</math> if <math>AUC_{(0-\infty)}</math> cannot be derived
 
• <math>C_{max}</math>
 

Model Specification

 
• For each endpoint a mixed model will be fit with 2 observations per subject expected. The model will contain state [[fed/faasted] as a fixed, categorical effect and a random intercept for subject.
 
• The Kenward & Roger (KR) degress of freedom approach will be used.
 

Model Checking & Diagnostics

 
• See Section 8.1.5.1
 

Model Results Presentation

 
• Point estimates and corresponding 90% CI will be computed for the differences in the endpoint for GSK2982772 MR formulation (120 mg) taken in the fed state (test) vs in the fasted state (reference) using the residual error from the model (MSE).
 
• The point and interval estimates on the log-scale will then be exponentially back transformed to give estimates of the ratios of geometric means, <math>F_{rel,FE}</math>, and 90% CI. See Section 10.6.4
 

Endpoint

 
• <math>T_{max}</math>
 

Model Specification

 
• Exact non-parametric Hodges-Lehmann estimation of location shift will be fitted.
 
• Only the dose of GSK2982772 administered under both fed and fasted conditions will be used.
 

Model Results Presentation

 
• GSK2982772 MR formulation in fed (test) will be compared to fasted (reference) state.
 
• Median difference and 90% CI for median difference will be presented.
 

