Descriptive statistics (n, arithmetic mean, standard deviation [SD], 95% CI, minimum, median and maximum,) will be calculated by treatment for all PK concentrations over time and for the derived PK parameters. In addition, for loge-transformed PK parameter variables geometric mean, 95% CI and $\%CV_b$ ($100 * \sqrt{(\exp(SD^2) - 1)}$) will be provided, where the SD is the standard deviation of log-transformed data.

Endpoint	Statistical Analysis Methods
Primary	
The primary PK endpoints to compare MR formulations with IR formulations will be summarised descriptively. Ratio of $AUC_{(0-inf)}$, $AUC_{(0-24)}$, ($AUC_{(0-t)}$, if $AUC_{(0-inf)}$ cannot be derived), C_{max}, C_{12} and C_{24} for MR formulation to IR formulation will be computed with 90% CI. C_{max} to C_{12h} and C_{max} to C_{24h} ratio for each MR formulation (120 mg or 240 mg) and the corresponding total dose of IR formulation (120 mg or 240 mg) will be computed with 90% CI.

Secondary	
The secondary endpoints for food effect will be summarised descriptively. In addition, log-transformed $AUC_{(0-inf)}$ ($AUC_{(0-t)}$, if $AUC_{(0-inf)}$ cannot be derived), C_{12h}, C_{24h}, and C_{max} will be analysed using a mixed effects model with regimen as a fixed effect and subject within sequence as a random effect. Point estimates and corresponding 90% CI will be computed for the differences for each GSK2982772 MR formulation (120 mg, 240 mg, 360 mg or 480 mg) taken in the fed state (test) vs the same dose in the fasted state (reference) using the residual error from the model (MSE). The point and interval estimates on the log-scale will then be exponentially back transformed to give estimates of the ratios of geometric means and 90% CI.
 
Within-subject coefficients of variation for $AUC_{(0-inf)}$ and C_{max} will be calculated based on the log_e-Normal distribution: $CV_w (\%) = \sqrt{\exp(mse) - 1} \times 100$, where MSE is the residual error from the model.
 
Statistical analysis of the PK endpoint T_{max} of each GSK2982772 MR formulation administered under both fed and fasted conditions will be separately analysed non-parametrically [Hauschke, 1990]. The point estimates for the medians for each treatment, the median difference and 90% CI for the median difference will be calculated for the contrast (test-reference).

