## 2. SUMMARY OF KEY PROTOCOL INFORMATION

### 2.1. Changes to the Protocol Defined Statistical Analysis Plan

There were no changes or deviations to the originally planned statistical analysis specified in the protocol (Dated: 07-Jul-2017).

Protocol amendment 1: There were no changes or deviations to the originally planned statistical analysis specified in the protocol (Dated: 18-Sep-2017).

Protocol amendment 2: Additional analyses were added for the inclusion of Part C that mirror what was specified for Part A (14-Jun-2018).

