### 8.2.5.3. Statistical Methodology Specification (Part C)

#### Bioavailability of Food Effect

Endpoint (log scale)

 
AUC(0-inf)
 
AUC(0-t) if AUC(0-inf) not available
 
Cmax
 

 

Model Specification

 
For each endpoint a mixed model will be fit with 5 observations per subject expected. The model will contain dose (240mg, 480mg) and prandial state [fed (standard)/delayed fed
 

(standard)/delayed fed (high-fat)/fasted] as a fixed, categorical effect and a random intercept for subject.

 
• A direct product (UN@CS) covariance pattern will be fit using dose and state (in that order) as the effects in the REPEATED statement.
 
• The Kenward & Roger (KR) degrees of freedom approach will be used.
 

Model Checking & Diagnostics

 
• See Section 8.1.5.1.
 

Model Results Presentation

 
• Point estimates and corresponding 90% CI will be computed for the differences in the endpoint for GSK2982772 MR formulation (240 mg or 480 mg) taken in the fed state (test) vs in the fasted state (reference) using the residual error from the model (MSE).
 
• The point and interval estimates on the log-scale will then be exponentially back transformed to give estimates of the ratios of geometric means, <math>F_{rel,FE}</math>, and 90% CI. See Section 10.6.4
 

Endpoint

 
• <math>T_{max}</math>
 

Model Specification

 
• Exact non-parametric Hodges-Lehmann estimation of location shift will be fitted.
 
• Only the dose of GSK2982772 administered under both fed and fasted conditions will be used.
 

Model Results Presentation

 
• GSK2982772 MR formulation in fed (test) state will be compared to fasted (reference) state.
 
• Median difference and 90% CI for median difference will be presented.
 

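### The SAP's food-effect models omit C24h, which the protocol says will be modelled, without declaring the removal; fed and fasted troughs are summarised but get no within-subject ratio or 90% CI

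*SAP*

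**What the plan says.** Protocol 10.4.1, in the secondary food-effect row, names log-transformed AUC(0-inf) (AUC(0-t) as fallback) and continues: "C_{12h}, C_{24h}, and C_{max} will be analysed using a mixed effects model with regimen as a fixed effect". It also fixes the output: model differences back-transformed to fed/fasted geometric mean ratios, each with a 90% CI. The two superseded protocol versions bound into the same file name the same endpoints.

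SAP 8.2.5.1 (Part A food effect) lists AUC(0-inf), AUC(0-t) as fallback, and Cmax on the log scale, then says: "For each endpoint a mixed model will be fit with 2 observations per subject expected". The food-effect block of SAP 8.2.5.3 (Part C) lists AUC(0-inf), then "AUC(0-t) if AUC(0-inf) not available", then Cmax, and says: "For each endpoint a mixed model will be fit with 5 observations per subject expected". Neither list contains C12h or C24h. Tmax is handled separately in both parts with a Hodges-Lehmann estimate and 90% CI.

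On changes from the protocol, SAP 2.1 says of the original protocol, and again of Amendment 1: "There were no changes or deviations to the originally planned statistical analysis specified in the protocol". For Amendment 2 it reports only that Part C analyses mirroring Part A were added.

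**The concern.** The product is being developed for once-daily dosing, so C24h is the trough. Protocol 3.1 says the slowest minitab suited once-daily dosing but was susceptible to a food effect, and that Part C should help decide whether a food restriction is needed. The fed/fasted trough ratio bears directly on that decision, and the protocol promised it with a 90% CI. The study tests no hypotheses, so estimates with intervals are its planned product.

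Separate geometric means with 95% CIs for each prandial state do not replace the ratio. Each of those intervals carries the between-subject variation that a within-subject comparison removes. The SAP version in hand already shows the treatments actually given (SAP 5.1), so a reader cannot tell when or why the endpoint left the model.

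**Working it through.** The plan gives no figure to reproduce here; the check is a comparison of texts.

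**Endpoints modelled, not counting the AUC(0-t) fallback**

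| Analysis | AUC | Cmax | C24h | C12h |
|---|---|---|---|---|
| Protocol 10.4.1, food effect | yes | yes | yes | yes |
| SAP 8.2.5.1, Part A food | yes | yes | no | no |
| SAP 8.2.5.3, Part C food | yes | yes | no | no |
| SAP 8.1.5.1, MR vs IR | yes | yes | yes | if BID |
| SAP 8.2.5.3, Part C dose | yes | yes | yes | no |

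Food effect goes from four modelled endpoints to two in each part, and SAP 2.1 declares no removals. C24h is modelled for MR versus IR and for dose, so only the food comparison lacks it.

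**Contrasts affected (SAP 5.1 labels).** Part A: 120 mg fed versus fasted, one. Part C: 480 mg fed (standard), 480 mg delayed fed (standard) and 240 mg delayed fed (high-fat), each against the same dose fasted, three. Total four.

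**What remains for C24h.** SAP 8.2.1.2 derives it for the food-effect periods, and SAP 8.2.2 gives descriptive statistics, geometric mean and 95% CI by prandial state. The Frel definition in SAP 10.6.4 uses AUC and Cmax only.

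**Would Cmax and Tmax stand in?** This is an illustration only. Assume zero-order release over T hours, complete absorption and one-compartment elimination with the 2 to 3 h half-life of Protocol 3.1. Then C at the end of release is proportional to (1 − e^(−kT))/T, followed by decline at rate k, and the AUC ratio is 1.0. If food cut release from 24 h to 12 h:

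- e^(−12k) = 2^(−4) = 0.0625 for a 3 h half-life, and 2^(−6) = 0.0156 for 2 h.
- C24h ratio = 2e^(−12k)/(1 + e^(−12k)) = 0.125/1.0625 = 0.118, and 0.03125/1.0156 = 0.031.
- Cmax ratio = 2/(1 + e^(−12k)) = 1.88 and 1.97. Tmax moves from 24 h to 12 h.

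If food cut release from 12 h to 6 h, the same algebra with e^(−6k) = 0.25 and 0.125 gives C24h ratios of 0.5/1.25 = 0.40 and 0.25/1.125 = 0.22.

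Cmax and Tmax would therefore show that something happened. They would not size the trough change: in the first scenario the two half-lives give Cmax ratios about 5% apart (1.97/1.88 = 1.05) and trough ratios nearly fourfold apart (0.118/0.031 = 3.8).

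**Likely precision.** The documents give no variability for C24h. Assume 12 completers and the within-subject CV range in Protocol 10.2 for AUC and Cmax (18.8% to 36.7%). With s = √ln(1 + CV²) and t(0.95, 11 df) = 1.796, the upper 90% limit is exp(1.796 × s × √(2/12)) times the estimate:

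- CV 18.8%: s = 0.186, factor 1.146.
- CV 36.7%: s = 0.355, factor 1.298.

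The upper limit would lie about 15% to 30% above the estimate. A trough concentration may vary more than this.

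**The case against.** The strongest case is that the protocol disagrees with itself. Its food-effect endpoint rows (Protocol 1 and 4) list AUC, Cmax, Tmax and Frel, not C12h or C24h. The SAP repeats those rows in 2.2 and its models match them. That stands as an explanation, but Protocol 10.4.1 specifies the analysis expressly, and a choice between the two belongs in SAP 2.1.

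For C12h the objection largely succeeds. SAP 2.4, in the MR-versus-IR paragraph, limits 12-hour parameters to BID dosing, and the notes to SAP 8.2.1.2 mark C12h as BID only for food effect. What remains is that the protocol has no such condition, SAP 2.1 does not mention it, and the food models omit C12h even under BID.

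A reader might infer that the food effect on the trough goes unreported. It does not: C24h is summarised by state, derived parameters are listed, and the interim package in Protocol 5.1.1 includes C24h and Cmax:C24h. A reader might also infer that a collapsed trough would escape the SAP. In the illustrated faster-release case the planned Cmax and Tmax contrasts would flag it.

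Two smaller points. Tables 3.6 and 3.19 are titled as covering AUC and C, but Part B Table 3.12 has the same title and its only modelled concentration endpoint is Cmax, so the title does not restore C24h. The Part C food list ends in an empty bullet, which could be text lost from the PDF. The Part C omission is therefore a little less certain than that in Part A, though SAP 2.1 says Part C mirrors Part A.

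**Conclusion.** The mismatch is real for C24h: four fed/fasted trough ratios with 90% CIs that the protocol specifies are missing from the SAP's models, and no removal is declared. It should be fixed, but it is not critical. The primary analyses are untouched, no hypothesis is tested, and the descriptive information survives. SAP 2.1 makes its no-change statement only for the original protocol and Amendment 1; for Amendment 2 it declares additions, so for Part C the fault is silence about a removal.

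The 3% to 12% fed/fasted trough ratio calculated above is an illustration resting on assumed zero-order release and an assumed halving of release time. The documents do not say that food halves release time, SAP 5.1 labels the products 12h, and a 12 h to 6 h change gives 22% to 40%. The conclusion needs none of these figures; it rests on the endpoint lists alone.

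**What to change.** - Add log C24h to the endpoint lists in SAP 8.2.5.1 and the Part C food block of 8.2.5.3, with back-transformed fed/fasted ratios and 90% CIs in Tables 3.6 and 3.19.
- State how non-quantifiable C24h values enter on the log scale. SAP 10.5.2 sets them to zero for concentration summaries, and zero has no logarithm; dropping them would lose the lowest troughs and bias the ratio. One option is to report the number non-quantifiable in each state and add a sensitivity analysis with a fixed substitution.
- Add C12h to the same lists if BID, and declare in SAP 2.1 that limiting it to BID departs from Protocol 10.4.1.
- If the sponsor prefers to leave C24h out, declare and justify that in SAP 2.1.

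The cost is one more run of an existing model in each part (two if C12h applies) plus the non-quantifiable rule. That rule is needed anyway, because the MR-versus-IR and dose models already include log C24h. No new data are required.
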